Our long-term goal is to establish effective therapies that restore function and improve mobility to enable increased levels of habitual physical activity for improved quality of life and longitudinal health outcomes in individuals with CP. The primary goal of this study is to validate the benefits of, and customer need for, differential and adjustable stiffness AFO features.

Our first aim is to confirm that the differential and adjustable stiffness (DAS) AFO improves plantarflexor push-off power and range of motion compared to standard (physician prescribed) AFOs during walking in CP.

Our second aim is to confirm that the differential and adjustable stiffness (DAS) AFO improves plantarflexor muscle activity while maintaining improved posture compared to standard AFOs during walking in CP.

Our third aim is to validate the need and usability of real-time stiffness adjustment during play and school activities; obtain feedback from the children, their parents, and orthotists to design the MVP.

Lay Summary:

This study seeks to determine how an adjustable stiffness ankle braces affects walking performance and biomechanics in cerebral palsy.

Resources:

This study will take place in the Biomechatronics Lab led by PI Assoc. [name]. Post-docs, graduate student researchers and undergraduate student researchers will be assisting with data collection and processing.

Population & Recruitment

- Maximum number of participants to be enrolled in the study: 11
- Please check all the categories of participants that will be included in the research:

 Children (1-17 yrs old)- Complete Appendix A	 Adults
 Prisoners- Complete Appendix C	 Refugees
 Native Americans - See the Tribal Consultation Policy	 NAU Staff/Faculty
 Pregnant Woman/ Neonates – Complete Appendix B	 NAU Students
 Cognitively Impaired Subjects	 Other- Explain Below

Project Narrative for Prospective Research

- What are the inclusion and exclusion criteria for study participation?

Inclusion Criteria:

- Age between 8-45 years old, inclusive
- Diagnosis of cerebral palsy (CP)
- Gross motor functional classification score level I, II, or III
- Physician-prescribed AFOs of common design (i.e., rigid molded thermoplastic)

Exclusion Criteria:

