Overview: We have developed a differential and adjustable stiffness AFO (DAS-AFO): Differential stiffnesses allows for customizing the stiffness in the plantarflexor and dorsal directions separately to maximize neuromuscular engagement and positive biological ankle power during push-off; A “real-time” stiffness adjusting slider allows for rapid and easy adjustment for different ambulatory conditions (e.g., walking, stairs, running). The primary goal of this study is to validate the benefits of, and need for, differential and adjustable stiffness AFO features. Our first aim is to confirm that the differential and adjustable stiffness AFO improves plantarflexor push-off power and range of motion compared to standard (physician prescribed) AFOs during walking in cerebral palsy (CP). Our second aim is to confirm that the differential and adjustable stiffness AFO improves plantarflexor muscle activity while maintaining improved posture compared to standard AFOs during walking in CP. Our third aim is to validate the need and usability for real-time stiffness adjustment during play and school activities; obtain feedback from the children and their parents.

Experimental Protocol for Aim 1 and 2: Participants will complete two 30-minute practice sessions, and a final assessment. On the final assessment, participants will walk on an instrumented treadmill for 6 minutes with their normal AFOs and with the DAS-AFO tuned to provide just enough dorsiflexor assistance to address drop foot (if present). Testing order will be block randomized. Treadmill speed will be set to each participant’s preference, as will the stance phase plantarflexor stiffness for the DAS-AFO.

Experimental Protocol for Aim 3: Participants will complete a series of play and school activities using the DAS-AFO and their normal AFOs; order will be block randomized. During the DAS-AFO condition, participants will be instructed to adjust stiffness using the simple slider as desired. Activities will include a series of floor-seated, chair-seated, standing, walking, and running (if applicable) tasks to capture the breadth of possible movements encountered during a typical school day. We will use video recording to observe and characterize interactions. These sessions will be followed by dedicated discussion time and validated product evaluation/usability questionnaires.

Outcome Measures: The following experimental data may be collected under each experimental protocol:

- Electromyography

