Principle Investigator

NCT06262191

December 18, 2024

Statistical Analysis Plan

Ankle joint kinematics and kinetics were calculated in OpenSim using the collected three-dimensional motion capture and the ground reaction forces. The joint kinematics and ground reaction forces were filtered using a low pass fourth order recursive Butterworth filter with a cut-off frequency of 6 Hz before being used to calculate joint kinetics. The ground reaction forces were collected using two force places associated with the instrumented treadmill (Bertec Corp, Columbus, USA) collected at 1200 Hz. The resultant joint kinetics were then further filtered using the same filtering parameters. Joint power was calculated as the product of the joint moment and joint angular velocity.

EMG was collected using wireless EMG sensors (Delsys Trigno, MA, USA). A sensor was placed on the soleus (SOL) muscle belly 2/3 of the distance between the medial condyle of the femur to the medial malleolus. We computed the linear envelope for each EMG signal by demeaning, bandpass filtering between 380 and 15 Hz (fourth-order Butterworth), and then low pass filtering the rectified signal with a cutoff of 7 Hz.

For EMG analysis, the integrated soleus muscle activity was computed during the last 50% of stance phase, and the integrated vastus lateralis EMG activity was quantified during the entire stance phase. To calculate the metabolic cost of transport, the standing baseline metabolic rate for each participant and each trial was subtracted from their walking metabolic rate to estimate the net metabolic rate of walking. Next, we normalized the net metabolic rate of walking by each participant's body mass and walking speed to calculate the metabolic cost of transport, averaged over the last two minutes of each condition. To quantify peak ankle push-off power, we identified the maximum ankle and hip power during the last 50% of the stance phase for each step.

To evaluate changes in our outcome measures, we used paired T-tests to test for differences in each outcome variable between the adjustable stiffness AFO and shod walking conditions. We tested for sphericity using Mauchly's test and used the Greenhouse-Geisser correction if data did not meet the sphericity assumption. Sidak adjusted p-values were used to reduce the chance of type I errors; the alpha level was set to .05. Partial eta squared was used to estimate effect size.

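### The SAP's only effect size, partial eta squared, is unsigned, unitless and positive on average under no effect, and its sphericity steps do not match the two-condition paired t-test it names

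*SAP*

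**What the plan says.** The SAP's final paragraph describes the whole inferential analysis. Its comparison is: "we used paired T-tests to test for differences in each outcome variable between the adjustable stiffness AFO and shod walking conditions". That is two conditions, hence one within-person difference per outcome.

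The next sentence reads: "We tested for sphericity using Mauchly's test and used the Greenhouse-Geisser correction if data did not meet the sphericity assumption". Multiplicity follows: "Sidak adjusted p-values were used to reduce the chance of type I errors; the alpha level was set to .05". The paragraph ends: "Partial eta squared was used to estimate effect size".

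It names no repeated-measures ANOVA, no factor with three or more levels, no mean difference and no confidence interval.

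In the protocol, the Aim 1 and 2 assessment also has two conditions: "participants will walk on an instrumented treadmill for 6 minutes with their normal AFOs and with the DAS-AFO". Aim 1 is directional: the device "improves plantarflexor push-off power and range of motion compared to standard (physician prescribed) AFOs during walking in CP". Aim 2 is directional for plantarflexor muscle activity too. Under Population & Recruitment the ceiling is: "Maximum number of participants to be enrolled in the study: 11".

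**The concern.** Two parts of the paragraph do not fit the test it names.

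First, sphericity is a condition on the variances of differences among three or more repeated measures. With a single pair there is nothing to test or correct. A reader cannot tell whether the sentence is left over from another analysis or is the only sign of a model that the SAP does not describe.

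Second, and more important, the trial asks whether the DAS-AFO improves push-off power, range of motion and muscle activity, and the only effect size named does not estimate an improvement. For a given n it is a function of |t| alone, so it adds nothing to the p-value about how large the change is in units of power, degrees or EMG. With at most 11 participants a p-value alone says little, and an estimate with its uncertainty is what a reader most needs. What is at stake is the reporting of size, direction and precision, not the outcome of the tests.

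**Working it through.** The documents give no expected effect, standard deviation or power, so there is no figure of the plan's own to reproduce. The check works from definitions.

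**Inputs.** Conditions compared: k = 2 (SAP, final paragraph). Pairs: at most n = 11 (Protocol, Population & Recruitment). The analysed n is not stated, so 6 to 11 is shown as an assumed range. The participant is taken as the unit of analysis, the paired differences as normal, and tests as two-sided, since the SAP does not state sidedness.

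**1. Sphericity steps.** Let C be the covariance matrix of the p = k − 1 orthonormal contrasts.

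- Mauchly's W = det(C) / (tr(C)/p)^p, with df = p(p + 1)/2 − 1.
- Greenhouse-Geisser ε = tr(C)² / (p · tr(C²)).
- k = 2: p = 1 and C is a single number c. So W = c/c = 1, df = 1·2/2 − 1 = 0 and ε = c²/c² = 1, whatever the data.
- k = 3: p = 2 and df = 2·3/2 − 1 = 2. In three simulated data sets with unequal variances ε ran from 0.61 to 0.71, so the correction would then do something.

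**2. Sign.** For a paired t-test, partial eta squared = t²/(t² + n − 1). At n = 11:

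- t = +2.5: 6.25/(6.25 + 10) = 0.385.
- t = −2.5: 6.25/(6.25 + 10) = 0.385.

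The signed standardised difference, t/√n, gives 2.5/√11 = +0.754 and −0.754.

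**3. Value when the device does nothing.** Under the null the index follows Beta(1/2, (n − 1)/2), whose mean is 0.5/(0.5 + (n − 1)/2) = 1/n. The true value is 0.

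| n | Null mean of partial eta squared |
|---|---|
| 11 | 0.5/5.5 = 0.091 |
| 10 | 0.100 |
| 8 | 0.125 |
| 6 | 0.167 |

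Simulation with 400,000 replicates at n = 11 gave a mean of 0.090. The null median there is 0.047 and the 95th percentile is 0.332. That percentile is the value at an unadjusted two-sided p of 0.05: with t = 2.228 on 10 df, 4.964/14.964 = 0.332.

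**4. The same check on a signed measure.** At n = 11 under the null, the mean difference divided by the SD of the differences averaged 0.000 in simulation, and it keeps its sign.

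**The case against.** The best case for the plan has three parts.

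*The sphericity steps may have a purpose.* The two documents together name three walking conditions: normal AFO and DAS-AFO in the protocol, and shod in the SAP. Mauchly's test, Greenhouse-Geisser, Sidak and partial eta squared are usual companions of a repeated-measures ANOVA. The SAP is written in the past tense, so the sentence may be the only trace of a three-condition model that was run. This stands as a reason to ask before deleting. It does not rescue the text as written, because no such model is described, and under one partial eta squared would still be unsigned and positive on average with no effect.

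*Direction and size are not lost.* The paired t-test has a sign, and the SAP does not exclude condition means. A reader might infer that the results will carry no direction and no figure in original units. The documents do not support that; they support only that none is specified.

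*No decision depends on the index.* Inference rests on Sidak-adjusted p-values at .05, and at fixed n partial eta squared is a one-to-one function of |t|. A reader might infer that its positive null mean produces false-positive findings. It does not: the 0.332 above is simply the unadjusted 5% point in another scale. Nor does the SAP set a benchmark above which the index counts as meaningful, so no rate of exceeding one can be drawn from the documents.

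All three narrow the point to estimation and clarity. None supplies the missing signed estimate or its interval.

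**Conclusion.** The point holds as one about the stated effect estimate and the coherence of the analysis text. For the two-condition test the SAP names, the sphericity steps have 0 df and a correction factor of 1, and removing them would alter no p-value. Partial eta squared gives the same value for benefit and harm (0.385 at t = ±2.5) and averages 1/n under no effect: 0.091 at 11 pairs, and more if fewer are analysed. It cannot serve as the estimate of a directional improvement.

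The 1/n result assumes normal paired differences with the participant as the unit. The absence of sign and units needs no assumption. The validity of the paired t-tests is not affected, and it is not established that the sphericity sentence is a mistake rather than part of an undescribed model. The change is worth making, but the hypothesis tests do not depend on it.

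**What to change.** 1. Replace partial eta squared as the effect estimate. For each outcome, report the mean within-person difference, DAS-AFO minus comparator, in the outcome's own units with a 95% confidence interval. With so few participants, the individual differences can be shown as well.
2. Before doing so, reconcile the comparator: the protocol's aims set the DAS-AFO against the standard AFO, while the SAP tests it against shod walking.
3. If a standardised size is wanted, use the signed mean difference over the SD of the differences, with a small-sample correction.
4. State which conditions and which model were analysed. If there are only two conditions, drop the Mauchly and Greenhouse-Geisser sentence. Keep it only if a repeated-measures model over three conditions is written into the SAP.

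The cost is SAP wording and a few columns in the results table. Every quantity comes from data already collected for the paired tests.
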